### a. Brief Summary

The purpose of this study is to assess the safety and ease of use of a trocar placement access device (TPAD, Tautona) for laparoscopic surgery. 10 patients will undergo laparoscopic surgery as planned, with their surgeon using the TPAD device to guide Veress needle insertion and primary trocar placement while gaining access to the peritoneal cavity. Surgeons will complete a questionnaire following use of the TPAD to evaluate the device feasibility. Ten patients will undergo standard of care without use of the TPAD device and also complete surveys.

---

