### a. Procedures

Surgeons will identify patients scheduled to undergo laparoscopic surgery procedures and notify study staff. The patient will be met in the pre- operative holding area and informed consent will be obtained.

Patients will be randomized via block randomization.

Clinical information will be collected from participating patients including age, sex, demographic, past medical and surgical history, medications, allergies, diagnosis, and planned procedure. Clinical data will be de- identified and stored on a password protected spreadsheet on a PHI- safe server.

The surgeon will utilize the TPAD device to assist with Veress needle insertion (standard of care) to obtain access to the peritoneal cavity. The device will also be used to guide primary trocar placement.

Following induction of general anesthesia, the patient is prepped and draped in sterile fashion. Local anesthetic is infiltrated at the planned incision site and an incision is made with a scalpel. These steps are the same in any laparoscopic procedure. Next, the sterile TPAD, which is connected to a suction source, is centered over the incision, and the suction cups activated to non-invasively grasp the skin. The TPAD is pulled upward, and the Veress needle is advanced through the incision into the peritoneal cavity. Once the needle enters the cavity, the abdomen is insufflated as per usual standard of care. Once insufflated, the veress needle is withdrawn while maintaining the TPAD's suction on the skin. The primary trocar is then advanced through the incision into the abdominal cavity. The suction is then released and the TPAD taken away from the operating field.

The time needed to obtain laparoscopic access and the time needed for trocar placement will be recorded. Non-identifiable photos and/or video may be taken of the TPAD device during use. Acquired digital images may capture a portion of the patient's skin, however if a patient has any identifying features such as scars or tattoos, these areas will be cropped out of the images, or if this is not possible, no images will be recorded of that patient. There will be no other alterations to the planned surgery and it will proceed as planned. Following surgery, the surgeon will complete a questionnaire. Any adverse events will be recorded by medical record review.

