**g. Study Endpoint(s)**

The study will terminate after 10 patients have been enrolled and have undergone surgery with use of the study device and 10 patients have undergone the standard of care and completed the survey. The primary outcome measure is device feasibility as measured by a surgeon questionnaire, which is completed at the end of every surgery. Secondary outcome measures include the time needed to obtain laparoscopic access using the device, as well as monitoring for adverse events. Another secondary outcome measure includes patient questionnaire to assess satisfaction.

If there is clear evidence of a lack of device feasibility through surgeon questionnaire review, or if there are any adverse events recorded that are related to the device and which endanger the health of a patient, the project leader will evaluate this information and decide whether any modifications or termination of the protocol are indicated.

---

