**g. Recruitment Details**

The surgeon will identify patients scheduled for laparoscopic surgery from their schedule and invite them to participate. If they are agreeable, study staff will be notified by the surgeon. The study staff will then meet the patient in the pre-operative area before their surgery to discuss the study and to obtain consent.

---

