**c. Procedures to Minimize Risk**

Risks will be minimized by adhering to the inclusion/exclusion criteria.

Postoperatively, patients will be cared for by the Stanford general surgery service which has expertise in the management of patients undergoing laparoscopic surgery.

All clinical data and images will be stored on an encrypted server. If the patient has identifying scars or tattoos, this will be cropped out of the images, or, if this is not possible, no images will be stored for that patient. All data will be coded with an assigned study number. The study key will be kept in a password protected file that will be deleted at the conclusion of the study.

---

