Pilot Study to Establish Safety and Ease of Use of a TauTona Pneumoperitoneum Assist Device (TPAD) for Laparoscopic Surgery

NCT04392635

August 19, 2024

Statistical Analysis Plan

Statistical Methods

For surgeon and patient questionnaire answers, a Wilcoxon test will be performed for each answer against a theoretical median of 4.0 (best). Since the insertion of the Veress needle should not significantly impact the final outcome of the entire laparoscopic procedure, analysis assumes that the theoretical median for each answer should be 4.0. Further, the standard of care is assumed to provide the current best care, so its theoretical median should be 4.0.

Determination of Sample Size

There were no statistically powered sample size requirements for this study. Based on the end points, the sample size of 15 for each group would be sufficient to determine bruising and the ability of the TPAD device to function as intended as compared to the control group.

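### One surgeon may supply several primary-outcome ratings, and the SAP's test of each answer against the best score, already hard to interpret, takes no account of this

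*Protocol*

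**What the plan says.** - **Outcome and rater.** Protocol 2.g defines the primary outcome as device feasibility, measured by "a surgeon questionnaire, which is completed at the end of every surgery". The surgery is the unit rated and the surgeon is the rater.
- **Recruitment.** Protocol 8.g: "The surgeon will identify patients scheduled for laparoscopic surgery from their schedule and invite them to participate". No section gives the number of surgeons or limits the cases each may contribute. Protocol 1.a speaks of surgeons in the plural, without a count.
- **Analysis.** The SAP, Statistical Methods, says "a Wilcoxon test will be performed for each answer against a theoretical median of 4.0 (best"). It gives the standard of care the same theoretical median. It mentions no surgeon term, clustering or repeated ratings, and states neither alpha nor sidedness.
- **Data.** Protocol 2.a lists the patient information to be collected, including "age, sex, demographic, past medical and surgical history, medications, allergies, diagnosis, and planned procedure", and also access and trocar times. The operating surgeon is not named there. The questionnaire form is not shown.
- **Size.** Protocol 1.a and 2.g plan 10 patients per arm. The SAP, Determination of Sample Size, gives 15 per group and says the size was not based on power.
- **Use of the ratings.** Under Protocol 2.g the project leader considers modifying or terminating the protocol "If there is clear evidence of a lack of device feasibility through surgeon questionnaire review".

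**The concern.** An ease-of-use score depends partly on who gives it. If one surgeon operates on several patients, that surgeon's scoring habit enters the test several times as though it were separate evidence. Low scores concentrated in one or two surgeons can then pass for a general problem with the device, and a run of 4s from a lenient surgeon can pass for broad acceptance.

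The conclusion on the primary outcome is at stake, and so is the mid-study review in Protocol 2.g. Whoever reads the questionnaires needs to know whether low scores come from one surgeon or from many, and the plan has no table that would show it.

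**Working it through.** **Inputs from the documents:** 15 ratings per arm (SAP) or 10 (Protocol); null value 4.0, labelled best. The SAP has no power calculation, so it offers no figure to reproduce.

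**Assumptions, none given in the documents:** one test per answer within each arm; zeros dropped; two-sided alpha 0.05; 3 or 5 surgeons with cases spread as evenly as possible; ICC 0.1, 0.3 or 0.5; a range of shares q of ratings below 4.

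**Step 1: what the test responds to.** No rating can exceed 4, so each difference from 4.0 is zero or negative. With k ratings below 4, all k signed ranks are negative and the exact two-sided p is 2/2^k:

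- k=5: 2/32 = 0.0625
- k=6: 2/64 = 0.031

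So p<0.05 first occurs at k=6, whatever the size of the shortfalls. In an arm of 15, six low ratings leave nine at 4, and the sample median is still 4.

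**Step 2: independent ratings.** P(k≥6) is a binomial tail.

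- n=15: 0.002 (q=10%), 0.061 (20%), 0.436 (35%), 0.739 (45%)
- n=10: below 0.001 (10%), 0.006 (20%), 0.166 (40%)

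At q=35% or 45% the true median is still 4, yet with 15 ratings the test rejects often. This happens without any clustering.

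**Step 3: ratings clustered by surgeon.** Each surgeon's count of low ratings is beta-binomial with a = q(1−ICC)/ICC and b = (1−q)(1−ICC)/ICC. The counts are convolved exactly over surgeons to give P(k≥6).

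| n per arm | q | Independent | 3 surgeons, ICC 0.1 / 0.3 / 0.5 | 5 surgeons, ICC 0.1 / 0.3 / 0.5 |
|---|---|---|---|---|
| 15 | 10% | 0.002 | 0.011 / 0.031 / 0.044 | 0.006 / 0.015 / 0.025 |
| 15 | 20% | 0.061 | 0.097 / 0.144 / 0.167 | 0.080 / 0.111 / 0.137 |
| 15 | 35% | 0.436 | 0.439 / 0.444 / 0.438 | 0.438 / 0.442 / 0.448 |
| 15 | 45% | 0.739 | 0.701 / 0.656 / 0.624 | 0.718 / 0.688 / 0.669 |
| 10 | 20% | 0.006 | 0.014 / 0.033 / 0.053 | 0.009 / 0.016 / 0.023 |
| 10 | 40% | 0.166 | 0.194 / 0.234 / 0.265 | 0.178 / 0.199 / 0.218 |

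Clustering raises the chance of rejection when low ratings are uncommon. At n=15 it leaves that chance about unchanged at 35% and lowers it at 45%.

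**Step 4: information content.** Effective n = n / [1 + (m−1)·ICC], with m cases per surgeon. For n=15 and 3 surgeons, m=5; at ICC 0.3 this gives 15/(1+4×0.3) = 15/2.2 = 6.8. Over the assumed range, 15 ratings are worth 5.0 to 12.5 independent ones and 10 are worth 4.5 to 9.1. With m=1 the divisor is 1 and nothing is lost.

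**Step 5: sensitivity to the form of the test.** The SAP does not say exact or approximate. If all low ratings tie at 3, the normal approximation with continuity correction first gives p<0.05 at k=5. The probability of k≥5 at q=20% goes from 0.164 to 0.184–0.285 (n=15) and from 0.033 to 0.041–0.105 (n=10). The direction is the same.

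**The case against.** The strongest reply is that clustering is not the main fault. Testing against the top of the scale already gives 0.436 at n=15 with independent ratings and 35% below 4, and clustering moves that only to 0.438–0.448. A surgeon adjustment alone would not repair the test. This stands, and it is why the fix makes the comparison descriptive.

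Second, at the Protocol's own 10 per arm the shift is small: at 20% low ratings, only 3 surgeons with ICC 0.5 takes the rejection chance above 0.05. This stands too. Third, the number of surgeons, the ICC and the share of low ratings are all assumed, so the figures show sensitivity and do not estimate what will happen in this trial.

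Three stronger readings are tempting, and the documents do not support them:

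- *The surgeon is not recorded.* Protocol 2.a lists patient information, introduces it as a non-exhaustive list, and the questionnaire form is not shown. Whether the surgeon is captured cannot be told.
- *Clustering always inflates false positives.* Under a symmetric null, simulation gives a type I error of 0.183 for n=15, 3 surgeons and ICC 0.3. That null cannot hold here, because no rating can exceed 4, and the effect in the table runs both ways.
- *A misleading p-value could stop the study.* Protocol 2.g refers to a review of questionnaires by the project leader and names no p-value or threshold. The SAP does not call these tests confirmatory.

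None of this removes the gap: the raters may repeat, and the plan neither allows for it nor reports it.

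**Conclusion.** The point holds in conditional form. The documents allow one surgeon to supply several ratings of the primary outcome, and the planned test assumes independence. Its p-values are hard to interpret in any case because the null is the best score; repeated surgeons would distort them further, by an amount and in a direction that depend on how common low ratings are. At 20% low ratings the shift is modest at 15 per arm and small at 10 per arm. These sizes rest on the assumed surgeon numbers, ICC, even spread of cases and two-sided 0.05. The documents do not establish that surgeons do repeat. This is an inexpensive improvement to consider for a pilot, not a fatal flaw.

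**What to change.** 1. Record a coded surgeon ID for every case. If it was not captured, take it from the operative record while cases can still be linked, since Protocol 9.c says: "The study key will be kept in a password protected file that will be deleted at the conclusion of the study". If the key is already gone, state this as a limitation.
2. Report the number of surgeons, cases per surgeon and arm, and ratings by surgeon and arm. Make the same table available for the questionnaire review in Protocol 2.g.
3. Amend the SAP so that per-arm results against 4.0 are descriptive, as counts at each score for each answer, with conclusions limited to the participating surgeons.

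The cost is one coded data field, one table and a change of SAP wording. The formal per-arm p-value is lost. With few surgeons the table could identify an individual, so codes are needed. Randomisation, sample size and surgical procedure are untouched.

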**3. BACKGROUND**

---

**a. Past Experimental and/or Clinical Findings**

Gaining laparoscopic access to the abdomen is a clinical challenge due to the nature of inserting surgical instruments through small incisions. Laparoscopic entry is a blind procedure and thus it is not surprising that at least 50% of major complications of laparoscopic surgery occur prior to the commencement of the intended surgery. This complication rate has remained stable for the past 25 years. The Hasson technique (open) is considered safer, but is more time consuming with an average access time of 3-10 minutes (Hasson 1999). The Veress technique is a blind technique that has the advantage of being faster, however carries a risk of major vascular injury during insertion (Sangrasi et al, 2011). It is critical during

Veress needle access to upward tension on the abdominal wall so as to increase the distance between the abdominal wall fascia and major abdominal blood vessels. In order to address this need, Tautona developed the TPAD, a device which applies suction to the abdominal wall skin to facilitate easy upward traction during Veress needle insertion, thus improving speed and safety of peritoneal access.

Sangrasi et al. A safe quick technique for placement of the first access port for creation of pneumoperitoneum. Journal of the Society of Laparoscopic and Robotic Surgeons. 2011

Hasson HM. Open laparoscopy as a method of access in laparoscopic surgery. Gynaecol Endosc. 1999;8:353–62.

---

**b. Findings from Past Animal Experiments**

N/A

---

**4. RADIOISOTOPES USED IN THE STUDY**

N/A

---

**5. DEVICES USED IN THE STUDY**

---

**a. Investigational Devices (Including Commercial Devices Used Off-Label)**

Investigational Device 1	
Name:	Trocar placement access device (TPAD)
Description:	The TPAD can be used to assist in the passage of a Veress Needle to establish a pneumoperitoneum for laparoscopic surgical procedures. The TPAD can also be used to place the Primary Trocar, once the pneumoperitoneum has been achieved. The TPAD is comprised of 1) a pad with suction cups throughout the bottom surface, 2) a port with which to connect to a line coming from a sterile central vacuum source (central vacuum line), 3) a feature to activate or deactivate the central vacuum line, and 4) a handle to manipulate the TPAD when suctioned to skin. The pad has a middle layer that distributes the vacuum from the central vacuum line to each of the suction cups.
Significant Risk? (Y/N)	No
Rationale for Non-Significant Risk	The device applies suction via small vacuum powered suction cups to the abdominal wall skin. the risk of injury due to use of the device is minimal. Peritoneal access is still achieved using a Veress needle, which is the standard of care.

---

**b. IDE-Exempt Devices**

N/A

---

**6. DRUGS, BIOLOGICS, REAGENTS, OR CHEMICALS USED IN THE STUDY**

N/A

---

**7. DISINFECTION PROCEDURES FOR MEDICAL EQUIPMENT USED ON BOTH HUMANS AND ANIMALS**

N/A

---

**8. PARTICIPANT POPULATION**

---

**a. Planned Enrollment**

(i) 30

(ii) 30

(iii) participants are patients undergoing laparoscopic surgery. The indications for laparoscopic surgery are very broad and include appendicitis, gallbladder disease, inflammatory bowel disease, cancer, and others.

---

**b. Age, Gender, and Ethnic Background**

Patients  $\geq$  18 years old of any gender and ethnicity will be recruited.

---

**c. Vulnerable Populations**

Patients who are economically/educationally disadvantaged, homeless, employees or students may be candidates to participate in the study. We will make it clear that participation is voluntary, that no part of their care is contingent on participating, and that there will be no compensation for participating. Decisionally impaired patients will not be included. Children and pregnant women will not be included in this pilot study.

---

**d. Rationale for Exclusion of Certain Populations**

No women or minorities will be excluded from participating. Children will not be included in this study as the device is primarily intended for use in adult patients.

---

**e. Stanford Populations**

We do not aim to recruit any particular number of laboratory personnel, employees and/or students. Participants may fall into these categories purely incidentally. All participants receive the same written informed consent.

---

**f. Healthy Volunteers**

There are no healthy volunteers as all participants have a clinical indication for undergoing laparoscopic surgery.

---

**g. Recruitment Details**

The surgeon will identify patients scheduled for laparoscopic surgery from their schedule and invite them to participate. If they are agreeable, study staff will be notified by the surgeon. The study staff will then meet the patient in the pre-operative area before their surgery to discuss the study and to obtain consent.

---

**h. Eligibility Criteria**

i. Inclusion Criteria

Age  $\geq$  18  
Scheduled for laparoscopic surgery  
Able to understand and willing to sign a written informed consent form

ii. **Exclusion Criteria**

Age < 18  
BMI > 35  
Any situation where blind, peri-umbilical passage of a Veress needle is contraindicated.  
Any situation where patients have suspected or confirmed intra-abdominal adhesions involving the peri-umbilical abdominal wall.  
Any situation where patients have a suspected or confirmed umbilical hernia or peri-umbilical ventral hernia.  
Any situation where there is not intact, uncompromised skin of the peri-umbilical region where the device is to be placed.

---

**i. Screening Procedures**

The surgeon will notify study staff of any patient meeting study inclusion criteria.

No personal health information will be collected prior to enrollment.

A waiver of authorization is provided in section 15. A data privacy attestation has been submitted.

---

**j. Participation in Multiple Protocols**

Patients will be asked if they are participating in any other studies prior to obtaining consent. If there is a potential that participation in either study may affect the outcome of the other, the patient will not be included.

---

**k. Payments to Participants**

No payment/reimbursement will be given for participation.

---

**l. Costs to Participants**

No additional costs are charged to the patient. the patient is still responsible for the cost of surgery.

---

**m. Planned Duration of the Study**

The study duration will be 1 year.

Total time per participant:

(i) screening: 1 week

(ii) active participation: <1 day (duration of surgery)

(iii) analysis of data: 1 month

---

## 9. RISKS

---

### a. Potential Risks

#### i. Investigational devices

The TPAD device contacts the abdominal skin through a series of small vacuum powered suction cups. These are only in contact with the skin for a few minutes. The risk of damage to the skin is minimal.

Obtaining peritoneal access with a Veress needle, as well as laparoscopic surgery in general, carries risks including bleeding, damage to underlying structures including injury to bowel or major blood vessels, hernia, infection, scarring, pain, need for additional procedures.

The risks of laparoscopic surgery include:

- Infection
- Bleeding
- Damage to surrounding structures
- Need for additional procedures
- Hernia
- Pain
- Scarring
- Wound healing problems

The risks of veress needle insertion include:

- failed entry
- omental injury
- organ injury
- insertion site infection

The risks of TPAD include:

- skin discoloration/bruising

#### ii. Investigational drugs

N/A

#### iii. Commercially available drugs, biologics, reagents or chemicals

N/A

#### iv. Procedures

The TPAD device contacts the abdominal skin through a series of small vacuum powered suction cups. These are only in contact with the skin for a few minutes. The risk of damage to the skin is minimal.

Obtaining peritoneal access with a Veress needle, as well as laparoscopic surgery in general, carries risks including bleeding, damage to underlying structures including injury

to bowel or major blood vessels, hernia, infection, scarring, pain, need for additional procedures.

Health information is collected, and there is a risk of loss of confidentiality. however, this risk is low, as this information is kept on encrypted, password-secured servers.

Intra-operative photos/videos taken will similarly be kept on a password protected, encrypted server. these images may include a portion of the patient's skin, but this will be un-identifiable. If the patient has identifying scars or tattoos, this will be cropped out of the images, or, if this is not possible, no images will be stored for that patient. thus, the risk of identity exposure from these images is very low.

v. Radioisotopes/radiation-producing machines

N/A

vi. Physical well-being

The TPAD device contacts the abdominal skin through a series of small vacuum powered suction cups. These are only in contact with the skin for a few minutes. The risk of damage to the skin is minimal.

Obtaining peritoneal access with a Veress needle, as well as laparoscopic surgery in general, carries risks including bleeding, damage to underlying structures including injury to bowel or major blood vessels, hernia, infection, scarring, pain, need for additional procedures.

vii. Psychological well-being

N/A

viii. Economic well-being

N/A

ix. Social well-being

N/A

x. Overall evaluation of risk

Medium

---

**b. International Research Risk Procedures**

N/A

---

**c. Procedures to Minimize Risk**

Risks will be minimized by adhering to the inclusion/exclusion criteria.

Postoperatively, patients will be cared for by the Stanford general surgery service which has expertise in the management of patients undergoing laparoscopic surgery.

All clinical data and images will be stored on an encrypted server. If the patient has identifying scars or tattoos, this will be cropped out of the images, or, if this is not possible, no images will be stored for that patient. All data will be coded with an assigned study number. The study key will be kept in a password protected file that will be deleted at the conclusion of the study.

---

